- ^e Planned to include approximately **CCI** post 1L patients with MET amplification/overexpression (FISH10+ and/or IHC90+) under CSP version 7.0 to receive savolitinib 300 mg bid + osimertinib 80 mg.

1L First line; 2/3L Second/third line; CSP Clinical study protocol; NA Not applicable.

Under CSP version 7.0, patients must have central confirmation of MET amplification and/or overexpression (FISH10+ and/or IHC90+) by FISH and IHC (central) testing. Pre-existing next generation sequencing (NGS) testing results are not accepted to enter Screening.

Provision of a formalin fixed and paraffin embedded (FFPE) tumour sample is mandatory.

Approximately **CCI** freshly cut (within **CCI** days) unstained sections (**CCI** micron) from FFPE tissue blocks or FFPE blocks containing equivalent material will be required per patient (refer to Central Laboratory Manual for detailed tissue requirements). Samples **CCI** years old will not be accepted.

Patients determined to be MET-amplified and/or overexpressed by FISH and IHC in Pre-screening will undergo screening during the 28 days prior to first administration of study medication to confirm eligibility (Sections 5.1 and 5.2).

Patients will continue to receive study medication in 28-day cycles until objective disease progression, unacceptable toxicity occurs, consent is withdrawn or another discontinuation criterion is met (Section 7). Patients may continue to receive treatment with osimertinib + savolitinib or osimertinib monotherapy (if savolitinib was stopped earlier) beyond RECIST 1.1-defined progression as long as they continue to receive clinical benefit, in the opinion of the investigator, and do not meet any of the discontinuation criteria (this may be beyond disease progression in the absence of clinical symptoms or signs indicating clinically significant disease progression; no decline in performance status; absence of rapid disease progression or threat to vital organs or critical anatomical sites [eg, CNS metastasis, respiratory failure due to tumour compression, spinal cord compression] requiring urgent alternative medical intervention; or no significant, unacceptable or irreversible toxicities related to study treatment) (Section 7.1). Patients can continue on savolitinib monotherapy (if osimertinib was stopped earlier or if randomised to the savolitinib + placebo arm) until objective disease progression. Savolitinib monotherapy post progression is not permitted.

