7 DISCONTINUATION OF STUDY INTERVENTION AND PATIENT DISCONTINUATION/WITHDRAWAL

7.1 Discontinuation of study intervention

Patients may be discontinued from IP in the following situations. Note that discontinuation from study treatment is NOT the same thing as a complete withdrawal from the study.

- Patient decision. The patient is at any time free to discontinue treatment, without prejudice to further treatment.
- Adverse events.
- Severe non-compliance with the Clinical Study Protocol.
- Objective disease progression as per RECIST 1.1. Patients may continue to receive treatment with osimertinib + savolitinib beyond RECIST 1.1-defined progression as long as they continue to receive clinical benefit, in the opinion of the investigator, and do not meet any of the discontinuation criteria.
- Patients incorrectly initiated on study medication.
- Pregnancy.
- Specific stopping criteria ie, ILD, acute anaphylaxis or QTcF interval prolongation with signs/symptoms of serious arrhythmia.

See the SoA ([Table 1](#) and [Table 2](#)) for data to be collected at the time of treatment discontinuation and follow-up and for any further evaluations that need to be completed.

Continuing on monotherapy

A patient can continue on savolitinib monotherapy (if osimertinib was stopped earlier or if randomised to the savolitinib plus placebo arm) until objective disease progression.

Savolitinib monotherapy beyond RECIST 1.1 progression is not permitted.

A patient who is originally randomised to savolitinib + osimertinib arm may continue to receive treatment with osimertinib monotherapy (if savolitinib was stopped earlier) beyond RECIST 1.1-defined progression as long as they continue to receive clinical benefit, in the opinion of the principal investigator and do not meet any of the discontinuation criteria (this may be beyond disease progression in the absence of clinical symptoms or signs indicating clinically significant disease progression; no decline in performance status; absence of rapid disease progression or threat to vital organs or critical anatomical sites [eg, central nervous system metastasis, respiratory failure due to tumour compression, spinal cord compression] requiring urgent alternative medical intervention; or no significant, unacceptable or irreversible toxicities related to study treatment), according to the SoA ([Table 1](#)).

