7.1.2 Procedures for discontinuation of study treatment

The investigator should instruct the patient to contact the site before or at the time if any study treatment is stopped. A patient that decides to discontinue study treatment(s) will always be asked about the reason(s) and the presence of any AEs. The date of last intake of study treatment(s) should be documented in the eCRF. All study treatment(s) should be returned by the patient at their next on-site study visit or unscheduled visit. Patients permanently discontinuing study treatment should be given locally available standard of care therapy, at the discretion of the investigator.

Discontinuation of study treatment(s), for any reason, does not impact on the patient's participation in the study. The patient should continue attending subsequent study visits and data collection should continue according to the study protocol. If the patient does not agree to continue in-person study visits, a modified follow-up must be arranged to ensure the collection of endpoints and safety information. This could be a telephone contact with the patient, a contact with a relative or treating physician, or information from medical records. The approach taken should be recorded in the medical records. A patient that agrees to modified follow-up is not considered to have withdrawn consent or to have withdrawn from the study.

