7.1.3 Follow-up of patients post discontinuation of study intervention

As a minimum, telephone contact should be made with the patient 28 days following the discontinuation of both IPs to collect new AEs and follow up on any ongoing AEs and concomitant medications (including any subsequent cancer therapy, if appropriate). Refer to Section 8.3.3 for full details on AE recordings during follow-up.

Patients who have discontinued study intervention prior to RECIST 1.1 defined radiological progression will be followed up with tumour assessments as indicated in the SoA until RECIST 1.1-defined PD or death regardless of whether or not the patient started a subsequent anti-cancer therapy, unless they have withdrawn all consent to study related assessments.

All patients will be followed for survival until the end of the study.

Patients who decline to return to the site for evaluations should be contacted by telephone as indicated in the SoA as an alternative.

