8.1 Efficacy assessments

8.1.1 CT and MRI scans tumour assessments (RECIST 1.1)

RECIST 1.1 guidelines for measurable, non-measurable, target lesions (TLs) and non-target lesions (NTLs) and the objective tumour response criteria are presented in [Appendix H](#) of this Clinical Study Protocol.

Baseline tumour assessments should include CT/MRI of chest and abdomen (including liver and adrenal glands) and should be performed within 28 days of treatment start, and ideally as close as possible to the start of study treatment.

At screening the MRI/CT scans will include brain imaging (MRI preferred) for all patients randomised under CSP version 7.0. Those determined to have brain metastases at baseline or those who had a history of brain metastases will have their brain rescanned at all subsequent tumour assessments (using the same modality as at baseline) until RECIST 1.1-defined PD, and lesions should be captured as non-target lesions in the RECIST 1.1 assessment. In patients without brain metastases at baseline and without a history of brain metastases, brain scans will be performed only when there is a suspected CNS progression and at the RECIST 1.1-defined extracranial progression. The brain scan is required for all patients at PD by investigator assessment per RECIST 1.1 and should be performed within 4 weeks, but preferably as soon as possible, to allow the assessment of new lesions in the brain. Any other regions suspected, or with known metastasis at baseline, will be assessed by imaging and recorded at baseline. The same imaging modality used for baseline tumour assessment should be used for each subsequent follow-up assessment throughout the study if possible. Further details of the CT and MRI acquisition parameters will be documented in a separate image acquisition guidelines document.

Follow-up assessments should be performed every 6 weeks (± 7 days) after the start of treatment until Cycle 7, and then every 8 weeks until objective disease progression as defined

by RECIST 1.1 even if a patient discontinues treatment prior to progression (unless they withdraw consent).

Patients randomised to the 300 mg bid savolitinib + placebo arm may cross over to 300 mg bid savolitinib + 80 mg od osimertinib following investigator assessed PD per RECIST 1.1. For patients who cross over after PD per RECIST 1.1, scheduled imaging is not required as specified in the crossover SoA ([Table 2](#)).

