8.4.5 Management of IP-related toxicities

8.4.5.1 Management of osimertinib-related toxicities

Potential osimertinib-related toxicities during the course of the study can be managed by interruption of the dose of osimertinib or dose reductions (see [Appendix I Section I 1](#)). Repeat dose interruptions are allowed as required. If a patient experiences a CTCAE Grade 3 (CTCAE version 5.0) and/or unacceptable toxicity, dosing will be interrupted and supportive therapy administered as required in accordance with local practice/guidelines. If the toxicity resolves or reverts to \leq CTCAE Grade 2 after 3 weeks of onset, treatment with osimertinib

may be restarted at the same dose (80 mg) or a lower dose (40 mg) using the rules in [Appendix I Section I 1](#) and with discussion and agreement with the AstraZeneca Study Team Physician as needed. There will be no individual modifications to dosing schedule in response to toxicity, only potential dose reduction or dose modification. If the toxicity does not resolve to \leq CTCAE Grade 2 after 3 weeks, then the patient should be withdrawn from the study and observed until resolution of the toxicity. Osimertinib can be dose reduced to 40 mg od: if the reduced dose of 40 mg od is not tolerable, no further dose reduction is allowed and study treatment should be discontinued. Once a dose is reduced escalation is not permitted.

Dose modifications are permitted in the management of IP-related toxicities as described in [Table 11](#) with further information being provided in [Appendix I Section I 1](#).

Dose modification guidelines for QTc prolongation are shown in [Table 12](#).

Table 11 Osimertinib dose adjustment information for adverse reactions

Target organ	Adverse reaction ^a	Dose modification
Pulmonary	ILD/pneumonitis	Permanently discontinue osimertinib
Other	Grade 3 or higher adverse reaction	Withhold osimertinib for up to 3 weeks
	If Grade 3 or higher adverse reaction improves to Grade 0 to 2 after withholding of osimertinib for up to 3 weeks	Osimertinib may be restarted at the same dose (80 mg) or a lower dose (40 mg)
	Grade 3 or higher adverse reaction that does not improve to Grade 0 to 2 after withholding for up to 3 weeks	Permanently discontinue osimertinib

^a The intensity of the clinical adverse events graded by the National Cancer Institute CTCAE Version 5.0.

ILD Interstitial lung disease.

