	Grade ≥ 3 adverse reaction that does not improve to Grade 0 – 2 after withholding osimertinib for up to 3 weeks	Permanently discontinue osimertinib

^a The intensity of the clinical adverse events graded by the NCI CTCAE version 5.0.

CTCAE Common Terminology Criteria for Adverse Events; ECG Electrocardiogram; ILD Interstitial lung disease; NCI National Cancer Institute.

I 1.1 ILD/Pneumonitis-like toxicity

If new or worsening pulmonary symptoms (eg, dyspnoea) or radiological abnormality suggestive of ILD is observed, an interruption in study treatment dosing is recommended, and the AstraZeneca study team should be informed. It is strongly recommended to perform a full diagnostic workup, to exclude alternative causes such as lymphangitic carcinomatosis, infection, allergy, cardiogenic oedema or pulmonary haemorrhage. The results of full diagnostic workup (including high resolution computed tomography (HRCT), blood and sputum culture, haematological parameters) will be captured by eCRF. All image data should be provided to AstraZeneca. In the presence of confirmatory HRCT scans where other causes of respiratory symptoms have been excluded, a diagnosis of interstitial lung disease should be considered and study treatment permanently discontinued.

I 1.2 QTcF prolongation

In light of the potential for QT changes associated with osimertinib, and in accordance with good clinical practice, it is recommended that correction of clinically significant electrolyte

abnormalities (hypokalaemia, hypomagnesaemia, hypocalcaemia) to within normal ranges takes place prior to first dose and during study treatment with osimertinib.

Table 21 Dose Modifications for Osimertinib-Related QTc Prolongation

NCI CTCAE version 5 toxicity grade	Action
Grade 0, 1, or 2	None
Grade 3	
Hold dosing and follow algorithm below
 
Patients with QTcF prolongation to > 500 msec on at least 2 separate ECGsIf the toxicity does not resolve to QTcF < 481 msec within 21 days
Grade 4	
QTcF \geq 501 or > 60 msec change from baseline and Torsade de pointes or polymorphic ventricular tachycardia or signs/symptoms of serious arrhythmia 
Discontinue osimertinib and consult with a cardiologist for further management as clinically indicated

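### Osimertinib toxicity unresolved at 3 weeks: Section 8.4.5.1 and Appendix I 1 order study withdrawal, where Tables 11 and 20 and Section 7.1 only stop osimertinib

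*Protocol*

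**What the plan says.** Protocol Section 8.4.5.1 covers a patient whose osimertinib toxicity has not come down to Grade 2 or lower after 3 weeks: "then the patient should be withdrawn from the study and observed until resolution of the toxicity". Appendix I 1 repeats the sentence and cites Table 20 at its end.

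The tables attached to those two places give a different action. Table 11 names the event as "Grade 3 or higher adverse reaction that does not improve to Grade 0 to 2 after withholding for up to 3 weeks" and Table 20 describes a Grade 3 or higher reaction "that does not improve to Grade 0 – 2 after withholding osimertinib for up to 3 weeks". In both, the action is permanent discontinuation of osimertinib, with nothing about leaving the study.

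The general rules side with the tables:

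- Section 7.1: "Note that discontinuation from study treatment is NOT the same thing as a complete withdrawal from the study".
- Section 4.1.1: "Patients can continue on savolitinib monotherapy (if osimertinib was stopped earlier or if randomised to the savolitinib + placebo arm"), until objective progression. Section 7.1 repeats this.
- Section 7.1.2, after treatment stops for any reason: "The patient should continue attending subsequent study visits and data collection should continue according to the study protocol".
- Section 7.1.3: tumour assessments go on to progression or death unless all consent to study assessments is withdrawn, and "All patients will be followed for survival until the end of the study".
- Section 8.1.1: scans continue "even if a patient discontinues treatment prior to progression (unless they withdraw consent").
- The footnote on tumour assessments in Table 1 (Schedule of Activities) and Appendix H 4.1 and H 4.5 say the same in substance.

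Appendix H 3.1 is the exception. It ends imaging at progression or at withdrawal from the study, where H 4.1 and H 4.5 refer to withdrawal of consent.

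**The concern.** Stopping a drug and leaving the study are different actions in this protocol. Section 7.3 describes study withdrawal as covering both investigational product and assessments. Taken literally, the sentence in 8.4.5.1 would end savolitinib, which the protocol otherwise allows to continue, and would end imaging before progression for a toxicity-related reason.

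Three endpoints could be touched. The primary objective response rate needs a confirming scan at least 4 weeks after the first response (SAP 3.2.1.1.2), so a patient whose imaging stopped after one responding scan would not count as a confirmed responder. Progression-free survival and duration of response are meant to run on regardless of withdrawal from therapy, and both could be censored instead. Protocol Section 6.3 says that withdrawn patients are not replaced.

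**Working it through.** **Action for the same event**

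| Place | Action |
|---|---|
| 8.4.5.1, text | Leave the study |
| Appendix I 1, text | Leave the study (then cites Table 20) |
| Table 11 | Stop osimertinib permanently |
| Table 20 | Stop osimertinib permanently |
| 4.1.1 and 7.1 | Savolitinib may continue alone |
| 7.1.2, 7.1.3, 8.1.1, Table 1 footnote, H 4.1, H 4.5 | Scans continue |
| H 3.1 | Scans end at study withdrawal |

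Two sentences stand against everything else, with H 3.1 the only place that would carry them through to imaging. No rule says whether text or table takes precedence. All of this is current text; none of it depends on redacted figures or the version history.

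**The 3-week limit**

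| Place | Limit | Starts at |
|---|---|---|
| 8.4.5.1, restart rule | *after* 3 weeks | onset |
| Appendix I 1, restart rule | *within* 3 weeks | onset |
| Tables 11 and 20, general rows | up to 3 weeks | withholding |
| Table 12, QTc, osimertinib | 21 days | onset |
| Table 20, QTc | 3 weeks | interruption |
| Table 21, QTc | 21 days | not stated |
| Table 25, QTc, osimertinib | 21 days | onset |

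*After* in 8.4.5.1 is a plain slip: read literally, it makes a patient who recovers early wait 3 weeks. The different starting points move the deadline only when onset and withholding differ.

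**When a first response could lose its confirmation**

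Inputs: scans every 6 weeks ±7 days up to week 24 (Table 1); confirmation at least 4 weeks later (SAP 3.2.1.1.2). Let *t* be the week in which the 3-week limit starts, from either onset or withholding. The limit ends at *t* + 3.

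- Nominal scans at weeks 6 and 12: 6 < *t* + 3 < 12, so *t* lies between weeks 3 and 9.
- Widest windows (scan 1 at week 5, scan 2 at week 13): 5 < *t* + 3 < 13, so *t* lies between weeks 2 and 10.
- Narrowest windows (scan 1 at week 7, scan 2 at week 11): 7 < *t* + 3 < 11, so *t* lies between weeks 4 and 8.
- The gap between the two scans is 11 − 7 = 4 weeks to 13 − 5 = 8 weeks, so scan 2 can serve as the confirming scan.

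If imaging stopped at the limit, a response first seen at scan 1 would have no confirming scan.

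**When an event would be censored**

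SAP 3.2.1.1.5 censors an event that follows two or more missed visits. The limit depends on the last evaluable scan:

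- baseline: 2 × 6 + 1 = 13 weeks
- visit 1 or 2: 2 × (6 + 1) = 14 weeks
- visit 3: (6 + 1) + (8 + 1) = 16 weeks
- visit 4 onward: 2 × (8 + 1) = 18 weeks

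For progression-free survival the range is therefore 13 to 18 weeks. On scheduled scans, a confirmed responder's last evaluable scan is visit 2 or later, so for duration of response it is 14 to 18 weeks. These limits matter only if a progression or death is recorded later. A patient with neither is censored at the last evaluable scan anyway.

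**The case against.** The best reply is that the protocol already answers the question. Appendix I 1 sends the reader to Table 20 in the disputed sentence itself, and 8.4.5.1 sends dose changes to Table 11. Both tables stop osimertinib only. Observing a patient until the toxicity resolves hardly fits a full exit from the study. Continued imaging is required in several places with no exception for toxicity. Section 7.3 describes study withdrawal as the patient's own request, for example by withdrawing consent; on that reading H 3.1 agrees with H 4.1. A site would have to set aside much of the protocol to do harm.

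Most of this stands. It shows that the intent was to stop treatment, and it is why the risk is small. It does not remove a contrary instruction from the text that a site consults when the event occurs. Nor is withdrawal confined to the patient's request elsewhere: Section 5 cites 7.3 for incorrectly enrolled patients, and Appendix C 2 withdraws a patient who withdraws sample consent. The SAP's deviation item 3.01 treats an adverse event as a dosing matter, but it is weak support, since the full deviation list is in a plan not supplied here.

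The SAP also limits the damage to the response rate. Item 7.04 lists a missed confirmation scan as an important deviation, and an additional analysis reports unconfirmed responses.

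On the clock, the reply largely succeeds. Dosing is to be interrupted when Grade 3 toxicity occurs, so onset and withholding should usually be close, and the timing result above does not depend on which is used. No effect of the different starting points on the results has been shown.

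**Conclusion.** The contradiction is real and should be corrected. Two sentences state the wrong rule; the tables and the general sections state the right one. The risk is limited and conditional: it needs a site to follow the sentence literally and to take study withdrawal as covering both drug and assessments.

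Its size cannot be given as a share of patients, because the documents report no rate of osimertinib toxicity unresolved at 3 weeks. What can be said is that a limit starting between weeks 3 and 9, at nominal scan dates, would end between scans 1 and 2.

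A reader might infer three stronger things that the documents do not support:

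- *Survival data would be lost.* Sections 7.1.3, 7.1.4 and 8.1.3 keep survival follow-up going, and 7.3 asks for vital status after withdrawal from public sources where local rules allow.
- *The randomised arms would be affected unequally.* No rates by arm are given, and the dose-reduction table for osimertinib (Table 8) also covers its placebo.
- *The primary response rate is materially biased.* Without a frequency, or evidence that any site acted this way, this cannot be concluded.

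**What to change.** - In 8.4.5.1 and Appendix I 1, replace the study-withdrawal instruction with permanent discontinuation of osimertinib (or placebo to osimertinib). Add that savolitinib may continue and that RECIST and survival follow-up continue under Sections 7.1 to 7.1.4.
- In H 3.1, replace withdrawal from the study with withdrawal of consent, to match H 4.1 and H 4.5.
- In the restart rule of 8.4.5.1, change *after* to *within* 3 weeks of onset.
- As a minor editorial point, if a single clock is adopted, apply it to 8.4.5.1, Appendix I 1 and Tables 11, 12, 20, 21 and 25 together. If withholding were chosen and Table 25 left alone, the edit would create a new conflict; Table 21 needs a stated start in any case.

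The cost is a wording amendment, with whatever ethics and regulatory approval Appendix A 1 requires. Sample size, visits and analyses do not change.

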8.4.5.2 Management of savolitinib-related toxicities

Potential savolitinib-related toxicities during the course of the study can be managed as medically indicated and with interruption of the dose of savolitinib or dose reductions as appropriate, **unless symptoms are associated with hypersensitivity** (see [Appendix I Section I 3](#)). Repeat dose interruptions are allowed as required, taking into consideration the additional precautions for restart of savolitinib as illustrated in [Appendix I](#). For each patient the savolitinib dose can be reduced a maximum of 2 times ([Table 9](#)). No dose re-escalations are allowed.

Dose modification guidelines for QTc prolongation are shown in [Table 12](#).

Table 12 Dose modifications for QTc prolongation

NCI CTCAE Toxicity Grade	Action with savolitinib	Action with osimertinib
Grade 0, 1, or 2	None	None
Grade 3 Patients with QTcF prolongation to >500 msec on at least 2 separate ECGs If the toxicity does not resolve to QTcF <481 msec within 21 days	Hold dosing and follow algorithm below: Consult with cardiologist to validate ECG finding. Ensure cardiac surveillance and take actions in accordance with clinical standards. Regular ECGs performed until resolution to QTcF <481 msec and then restart drug at one reduced dose level.* Permanently discontinue study drug and consult with a cardiologist for further management as clinically indicated.	Hold dosing and follow algorithm below: Withhold until QTc interval is <481 msec or recovery to baseline if baseline QTc is more than 481 msec within 21 days of onset, then restart at a reduced dose (40 mg) or at 80 mg (at the discretion of the investigator). Permanently discontinue osimertinib.
Grade 4 QTcF \geq 501 or >60 msecs change from baseline and Torsade de pointes or polymorphic ventricular tachycardia or signs/symptoms of serious arrhythmia	Permanently discontinue study drug and consult with a cardiologist for further management as clinically indicated.	Permanently discontinue osimertinib.

CTCAE Common Terminology Criteria for Adverse Events; ECG Electrocardiogram; NCI National Cancer Institute; QTc corrected QT interval; QTcF corrected QT interval using Fridericia's formulas.

***For French sites only**, as per ANSM advice, the patient must remain hospitalised with continuous cardiac monitoring (ECG) until specialist advice is obtained by a cardiologist.

